3.6 Study treatment

Duration of study treatment exposure, cumulative dose, dose intensity (DI) and relative dose intensity (RDI) will be summarized by treatment. In addition, the duration of exposure to study treatment will be categorized into time intervals; frequency counts and percentages will be presented for the number of patients in each interval. The number of patients, who have dose reductions or interruptions, and the reasons, will be summarized by treatment.

Listings of all doses of the study treatment along with dose change reasons will be produced.

The Safety Set will be used for all summaries and listings of study treatment.

3.6.1 Duration of study treatment exposure

The following algorithm will be used for everolimus and exemestane to calculate the duration of study treatment exposure for patients who took at least one dose of any of the components of the study treatment:

Duration of exposure (days) = (date of last administration of study treatment) – (date of first administration of study treatment) + 1.

For capecitabine, the duration of exposure will include the rest periods and will be then defined as:

Duration of exposure (days) = (date of last administration of study treatment) – (date of first administration of study treatment) + 7 days (corresponding to the theoretical rest period) + 1.

The duration includes the periods of temporary interruption (of any component of the study treatment for any reason).

Duration of exposure to each component of the study treatment will also be calculated.

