### 6.1.1 Dosing regimen

Patients will be randomly assigned with equal allocation to one of the treatment arms below:

- a. Everolimus in combination with exemestane
- b. Everolimus monotherapy
- c. Capecitabine monotherapy

Table 6-1 Dose and treatment schedule

Study drugs	Pharmaceutical form and route of administration	Dose	Frequency and/or Regimen
Everolimus	Tablets for oral use	10 mg (2 × 5 mg)	Daily
Exemestane	Tablets for oral use	25 mg	Daily
Capecitabine	Tablets for oral use	1250 mg/m 	Twice daily for 2 weeks followed by one week rest (3-week cycle)

Everolimus (RAD001) will be self-administered by continuous oral daily dosing of  $2 \times 5$  mg tablets. Everolimus should be taken at the same time every day. Everolimus tablets should be swallowed whole with a glass of water once daily, either consistently with food or consistently without food. Tablets should not be chewed or crushed.

Capecitabine and exemestane will be self-administered as described in Table 6-1 in accordance with the local label in participating countries.

Everolimus 10 mg (2 x 5 mg) and exemestane 25 mg should be taken together at the same time every day.

If patients realize they missed a dose of study medications (everolimus, exemestane) within 6 hours following the scheduled dosing time point, they should take the missed dose of the study medication(s). If patients realize they missed a dose more than 6 hours following the

Protocol No. CRAD001Y2201

scheduled dosing time point, then patients should skip the missed dose(s). For missing dose of capecitabine, please refer to the local product information.

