2.1.5 Date of last administration of study treatment

The date of last administration of study treatment is defined as the last date when a non-zero dose of any component of study treatment was administered and recorded on the DAR eCRF.

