3.6.3 Dose intensity and relative dose intensity

Dose intensity (DI) for patients with non-zero duration of exposure is defined as follows:

DI (dosing unit / unit of time) = Cumulative dose (dosing unit) / Duration of exposure (unit of time).

For patients who do not receive any drug, the DI will be set to zero.

Planned dose intensity (PDI) is the assigned dose by unit of time planned to be given to patients as per protocol in the same dose unit and unit of time as that of the Dose Intensity.

For Capecitabine, the planned dose recommended as per protocol is 1250 mg/m² twice daily for 14-days every 3 weeks (i.e. 3-week cycle). The planned dose intensity including the rest period of 7 days is calculated as:

PDI (Cap.) = 1250 mg/m²*2*14 days / 21 days = 1666.67 mg/m²/day.

Relative dose intensity (RDI) is defined as follows:

RDI = DI (dosing unit / unit of time) / PDI (dosing unit / unit of time).

DI and RDI will be summarized separately for each of the study treatment components, but using the duration of the study treatment exposure, not the duration of exposure to each of the components.

For the calculation of the assigned body-surface-area-adjusted capecitabine dose at every cycle, the following formula will be used:

$BSA [m^2] = 234.94 * (\text{height}[cm]**0.422) * (\text{weight}[kg]**0.515) / 10000.$

according to the height at baseline and the last available weight at or before the cycle start date.

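### The fixed 7-day rest added to capecitabine exposure gives fully compliant patients who stop mid-course a relative dose intensity below 1 and an overstated duration

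*SAP*

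**What the plan says.** The current capecitabine rule entered the SAP through Addendum 1, dated 27 October 2017 and marked as after database lock, so that rest periods would be counted. SAP 3.6.1 introduces it thus: "For capecitabine, the duration of exposure will include the rest periods and will be then defined as". The definition is the last administration date minus the first, plus "7 days (corresponding to the theoretical rest period) + 1". No condition is placed on where in the cycle dosing stopped. SAP 2.1.5 takes the last administration to be "the last date when a non-zero dose of any component of study treatment was administered", so it can be any of the 14 dosing days.

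SAP 3.6.3 divides cumulative dose by this duration to give dose intensity (DI), and divides DI by planned dose intensity (PDI) to give RDI. The schedule is "1250 mg/m² twice daily for 14-days every 3 weeks", as in Protocol 6.1.1, and the planned figure is averaged over the whole cycle: "PDI (Cap.) = 1250 mg/m²*2*14 days / 21 days = 1666.67 mg/m²/day".

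Neither section has a rule for a last course that ends before day 14.

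**The concern.** The PDI spreads 14 days of dosing over 21 days, so it assumes two dosing days for each rest day. The duration adds a full rest week even when only part of the last dosing phase was given. Numerator and denominator then cover different stretches of the planned calendar, and a patient who took everything scheduled up to her last dose appears under-dosed.

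The distortion is largest in patients who stop in the first cycle or two, where a low RDI could be misread as poor delivery of the drug. SAP 3.6 also groups duration into time intervals, so some mid-course stops may be counted in a longer interval than they belong in. The summaries are presented by treatment, and the artefact sits in the capecitabine arm alone. The addendum was written to correct these same quantities.

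**Working it through.** **Inputs.** Daily dose on dosing days: 1250 × 2 = 2500 mg/m² (SAP 3.6.3). Cycle: 14 days on, 7 off (Protocol 6.1.1, Table 6-1). Duration: last date − first date + 7 + 1 (SAP 3.6.1). DI = cumulative dose / duration and RDI = DI / PDI (SAP 3.6.3).

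**Step 1: the SAP's own figure.** PDI = 2500 × 14 / 21 = 35,000 / 21 = 1666.67 mg/m²/day, which agrees with the SAP.

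**Step 2: a fully compliant patient.** She takes every scheduled dose, without delay, and her last dose is on dosing day d (1 to 14) of cycle k.

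- Cumulative dose = 2500 × [14(k−1) + d]
- Last date − first date = 21(k−1) + d − 1
- SAP duration = 21(k−1) + d + 7
- Since 2500 / 1666.67 = 1.5, RDI = [21(k−1) + 1.5d] / [21(k−1) + d + 7]

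This is below 1 exactly when 1.5d < d + 7, that is, when d < 14. At d = 14 it equals 1 in every cycle. No assumption about stopping times is needed for this result.

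**Step 3: numbers, last dose on day 5.**

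- Cycle 1: 12,500 mg/m² over 12 days gives DI 1041.67 and RDI 0.625.
- Cycle 2: 47,500 over 33 days gives DI 1439.39 and RDI 0.864.
- Cycle 8: 257,500 over 159 days gives DI 1619.50 and RDI 0.972.

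RDI for other days of last dose:

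| Cycle | Day 1 | Day 7 | Day 13 | Day 14 |
|---|---|---|---|---|
| 1 | 0.188 | 0.750 | 0.975 | 1.000 |
| 2 | 0.776 | 0.900 | 0.988 | 1.000 |
| 6 | 0.942 | 0.971 | 0.996 | 1.000 |
| 8 | 0.958 | 0.978 | 0.997 | 1.000 |

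**Step 4: effect on the arm mean.** The documents do not give the share of mid-course stops, so this step is assumption. I took perfect compliance, exponential time on drug, and stops in the rest week counted as a last dose on day 14. A 6-month median equals the SAP's planning median for PFS on capecitabine; it is not a documented time on drug.

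- Stops unrelated to the schedule, medians of 3, 6 and 9 months: mean RDI 0.947, 0.968 and 0.977, with 12.8%, 6.8% and 4.6% of patients below 0.90.
- In the 6-month case, the 15% who stop within 42 days average 0.864, while the median RDI over all patients is 0.994.
- If 50% or 70% of stops instead wait for the next 6-weekly scan (6 weeks is two full cycles, so the last dose is then day 14), the 6-month means become 0.984 and 0.990, with 3.4% and 2.1% below 0.90. Over medians of 3 to 9 months the range is about 0.97 to 0.99.

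**The case against.** The strongest reply is that this is a convention. The SAP labels the 7 days theoretical and defines the plan by whole cycles; a patient who abandons a course on day 5 did not receive that course, so a value below 1 is defensible. That would hold if the whole course were charged. But the whole-course ratio for a cycle 1 day 5 stop is 5/14 = 0.36, and the ratio to doses scheduled so far is 1. The SAP's 0.63 is neither, because it charges the rest week but not the nine dosing days still to come.

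Several points on the other side stand:

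- Tumor assessments fall every 6 weeks, so stops at a scan tend to land in a rest week, where the formula is right. The ±7-day window could move some back into a dosing phase, so the arm-level figure stays uncertain.
- Everolimus and exemestane carry no added days because they are dosed continuously. That contrast shows where the artefact is confined; it is not evidence of an error.
- A reader might infer that RDI and duration are the only record of capecitabine delivered. They are not: SAP 3.6, 3.6.2 and 3.6.4 also report cumulative dose, reductions and interruptions with reasons, and listings of all doses. The 7-day term touches none of these.
- A reader might also infer that every compliant patient is under-reported, or that the efficacy comparison is affected. A last dose on day 14 is handled exactly, and exposure does not enter the PFS or OS analyses.

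**Conclusion.** The point holds for patients whose last capecitabine dose falls on days 1 to 13 of a cycle, including any who are mid-course at the data cut-off. Their RDI is understated and their duration overstated. For a day 5 stop in cycle 1, the SAP duration is 12 days against 7.5 with a rest in proportion to the dosing given. The error is large in cycle 1, falls to 3% or less for a day 7 stop from cycle 6 on, and is zero for completed courses.

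That much is algebra. The effect on the arm mean is not: 0.95 to 0.98 if stops are unrelated to the schedule, and 0.97 to 0.99 if 50% to 70% coincide with scans, in both cases assuming exponential time on drug with a median of 3 to 9 months and perfect compliance. The matter is minor and confined to the descriptive capecitabine duration, DI and RDI summaries.

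**What to change.** **RDI.** In SAP 3.6.3, define capecitabine RDI as cumulative dose divided by the cumulative dose planned up to the last dosing day on the 14-on/7-off calendar. For a fully compliant patient both are 2500 × [14(k−1) + d], so RDI is 1 wherever she stops.

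**Duration and DI.** In SAP 3.6.1, replace the fixed 7 days with half the dosing days elapsed in the last course, reaching 7 only when all 14 are completed. Duration becomes 21(k−1) + 1.5d. For cycle 1 day 5 that is 7.5 days, and DI = 12,500 / 7.5 = 1666.67, equal to PDI. Duration, DI and PDI then agree.

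**What to avoid.** Do not simply drop the 7 days for mid-course stops while keeping the PDI, because that reverses the bias. DI/PDI would be 1.5d/d = 1.50 for any cycle 1 stop on days 1 to 13, and 31.5/28 = 1.125 for cycle 2 day 7.

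The SAP should also state how a delayed cycle counts in the planned calendar, since the two definitions are shown here to agree only for patients on schedule.

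**Cost.** A short change to the exposure formulas in the SAP and one program change, using dose records already collected. No new data are needed.

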3.6.2 Cumulative dose

Cumulative dose is defined as the total dose given during the study treatment exposure period and will be summarized for each of the study treatment components separately. For patients who do not receive any drug, the cumulative dose will be set to zero.

3.6.3 Dose intensity and relative dose intensity

Dose intensity (DI) for patients with non-zero duration of exposure is defined as follows:

DI (dosing unit / unit of time) = Cumulative dose (dosing unit) / Duration of exposure (unit of time).

For patients who do not receive any drug, the DI will be set to zero.

Planned dose intensity (PDI) is the assigned dose by unit of time planned to be given to patients as per protocol in the same dose unit and unit of time as that of the Dose Intensity.

For Capecitabine, the planned dose recommended as per protocol is 1250 mg/m² twice daily for 14-days every 3 weeks (i.e. 3-week cycle). The planned dose intensity including the rest period of 7 days is calculated as:

PDI (Cap.) = 1250 mg/m²*2*14 days / 21 days = 1666.67 mg/m²/day.

Relative dose intensity (RDI) is defined as follows:

RDI = DI (dosing unit / unit of time) / PDI (dosing unit / unit of time).

DI and RDI will be summarized separately for each of the study treatment components, but using the duration of the study treatment exposure, not the duration of exposure to each of the components.

For the calculation of the assigned body-surface-area-adjusted capecitabine dose at every cycle, the following formula will be used:

$BSA [m^2] = 234.94 * (\text{height}[cm]**0.422) * (\text{weight}[kg]**0.515) / 10000.$

according to the height at baseline and the last available weight at or before the cycle start date.

3.7 Concomitant therapy

Concomitant therapy is defined as all interventions (therapeutic treatments and procedures) besides the study treatment that were administered to a patient, preceding or coinciding with the study assessment period.

Concomitant medications entered into the database will be coded using the WHO Drug Reference List to allow for categorization by preferred term. In addition to categorizing medication data by preferred term, drugs will be classified according to their ATC classification in order to present and compare how they are being utilized.

Concomitant medications and significant non-drug therapies taken concurrently with the study drug(s) will be listed and summarized by ATC class, preferred term and treatment arm by

means of frequency counts and percentages. These summaries will include medications starting on or after the start of study treatment or medications starting prior to the start of study treatment and continuing after the start of study treatment.

Any prior concomitant medications or significant non-drug therapies starting and ending prior to the start of study treatment will be listed.

The Safety Set will be used for all concomitant medication tables and listings.

Concomitant medications that have the potential to impact some specific analyses (e.g., efficacy analyses) will be identified prior to database lock. Separate summaries of these concomitant medications will be produced and the corresponding analysis populations will be used. Strong and moderate inhibitors, inducers, or substrates of the isoenzyme CYP3A will be identified as described in [Section 2.4.1](#). The strong ones will be tabulated by ATC code. Both strong and moderate ones will be listed. New anti-neoplastic therapies will be listed based on their identification (by the method given in [Section 2.4.2](#)) by the protocol deviation process.

Anti-neoplastic therapies since discontinuation of study drug will be listed and summarized by ATC class, preferred term and treatment arm by means of frequency counts and percentages in separate summaries using the Full Analysis Set. In addition, the first regimen with combination of several drugs if any after the study treatment discontinuation will be summarized by treatment arms, using the full analysis set population.

3.8 Efficacy evaluation

The efficacy endpoints based on tumor assessments will be derived according to RECIST 1.1 (see [Appendix 1 of the study protocol](#) for details). The tumor endpoint derivation is based on the sequence of overall lesion responses at each assessment/time point. The overall lesion response at a given assessment/time point will be provided by the local (treating center's) radiologist/investigator. In particular, the final local (treating center's) radiologist's/investigator's visit response for each assessment/time point collected on the RECIST 1.1 overall lesion response CRF page will be used to derive the primary efficacy endpoint. The tumor assessment dates will be derived by Novartis using the dates of the individual lesion measurements.

Data included in efficacy analyses

Efficacy analyses will include all data observed in patients from the FAS regardless of whether the data were observed on-treatment or after the study treatment discontinuation until the analysis cut-off date. In particular, the "30 days" rule applied to all safety analyses will NOT be used for efficacy analyses.

For patients who took other anti-neoplastic drugs, their efficacy data (other than overall survival) will be censored so that the tumor assessments made after the administration of the other anti-neoplastic drugs are not included in the primary efficacy analyses.

For patients with protocol deviation code C17 ("Lack of PI oversight and no eCRF signatures at Database Lock (DBL) due to PI departure and no replacement"), efficacy data will be analyzed as follows:

- Progression-Free Survival will be censored at randomization date with censoring reason “Adequate assessment no longer available”
- Overall Survival will be censored at randomization date with censoring reason “Lost to follow-up”
- Best Overall Response will be set to UNK with reason “No valid post-baseline assessment”
- Overall Response status as non-responder
- Clinical Benefit status as non-responder

3.8.1 Primary Efficacy

Progression-free survival (PFS) derived from an investigator’s assessment of radiology data will be used as the primary efficacy variable. The PFS is defined as the time from the date of randomization to the date of the first documented disease progression or death due to any cause, whichever occurs first. If a patient has not progressed or died at the analysis cut-off date, or if she receives any further anti-neoplastic therapy, PFS will be censored at the time of the last tumor assessment before the cut-off date or the anti-neoplastic therapy date whichever occurs first. Further anti-neoplastic therapies will be identified via protocol deviations and from data collected on ‘Antineoplastic therapies since discontinuation of study drug’ eCRF. Definitions and further details on PFS can be found in [Appendix 1 of the protocol](#).

Discontinuation due to disease progression (collected on the “End of treatment” and “Study Evaluation Completion” page) without supporting objective evidence satisfying progression criteria per RECIST 1.1 will not be considered a progressive disease.

Primary analysis

The primary objective of this study is to estimate the hazard ratio of a progression-free survival event comparing the everolimus + exemestane combination therapy with the everolimus monotherapy in postmenopausal women with ER-positive, HER2-negative, advanced breast cancer (ABC) after recurrence or progression on letrozole or anastrozole.

The primary analysis of PFS will be based on data from investigator/local radiology review. The analysis will be performed on the FAS following the intention-to-treat (ITT) principle, i.e., patients will be analyzed according to the treatment group they were randomized and the stratum they were assigned to at baseline. The analysis will use the default censoring and event date definitions from Table 3-1 of Appendix 1 of the study protocol, i.e. A(1), B(1), C1(1), C2(1), D(1), E(1), and F(1). In particular, PFS will be censored at the last adequate tumor assessment if one of the following occurs: absence of a PFS event; a PFS event occurs after a new anticancer therapy is given; a PFS event occurs after two or more missing tumor assessments (see [Section 2.5.5](#)). Discontinuation of study treatment (for any reason) will not be considered as a reason for censoring.

Kaplan-Meier estimates

The Kaplan-Meier (KM) estimate of the progression-free survival function will be computed for each treatment group using PROC LIFETEST with method=KM option in SAS. The results will also be plotted graphically (Kaplan-Meier curves) by treatment and by randomization strata as assigned through IRT. The plots will display the number of patients at risk at equidistant time points.

The estimated median PFS for each treatment group will be provided along with the approximate 90% confidence intervals (Brookmeyer and Crowley, 1982). Additionally, the 25th and 75th percentiles will also be computed. The progression-free survival probabilities at 2, 4, 6 and 9 months (timepoints to be adapted depending on the length of the follow-up), along with 90% confidence intervals, will be presented by treatment group. The log-log transformation available within PROC LIFETEST will be used to compute the confidence intervals.

Hazard ratio estimate

The hazard ratio estimate of a PFS event comparing the everolimus + exemestane combination therapy with everolimus monotherapy, along with the two-sided 90% confidence interval, will be obtained from the stratified Cox proportional hazards model, fitted using SAS PHREG procedure with ties=EXACT option and the stratification information obtained through IRT. In the PHREG procedure, the MODEL statement will include the indicator of assignment to the everolimus + exemestane arm as the only covariate. The baseline hazard function will be allowed to vary across strata, i.e., the STRATA statement will include the stratification variable obtained through IRT.

Sensitivity and other supportive analyses of the primary endpoint PFS

To assess the impact of stratification, a sensitivity analysis will be performed to estimate the PFS treatment effect (everolimus + exemestane versus everolimus alone) using the unstratified Cox regression model yielding the hazard ratio estimate of a PFS event along with the 90% confidence interval.

The following sensitivity PFS analyses will be performed to assess the impact of missing/unknown tumor assessments (analyses 1 and 2 below) and to assess the impact of PFS censoring due to another anti-neoplastic therapy (analysis 3 below):

- PFS using local radiology assessments on the FAS and using the following options in Table 14-5 on page 121 of [Appendix 1 in the study protocol](#): A(1), B(1), C1(1), C2(3), D(1), E(1), and F(1), i.e., taking the event whenever it occurs even after two or more missing tumor assessments (see [Section 2.5.5](#)). In the summary table, this approach will be referred to as the ‘actual event PFS analysis’.
- PFS using local radiology assessments on the FAS and using the following options in Table 14-5 on page 121 of [Appendix 1 in the study protocol](#): A(1), B(1), C1(2), C2(2), D(1), E(1), and F(1), i.e., backdating of events occurring after missing tumor assessments. In the summary tables, this approach will be referred to as the ‘backdating PFS analysis’.
- PFS using local radiology assessments on the FAS and using the following options in Table 14-5 on page 121 of [Appendix 1 in the study protocol](#): A(1), B(1), C1(1), C2(1),

D(1), E(1), and F(4), i.e., and not censoring patients at the start of new anti-neoplastic therapies (if tumor assessment data are available following the start of new anti-neoplastic therapies).

A multivariate stratified Cox regression model will be used to evaluate the effect of baseline demographic and disease characteristics of potential prognostic value on PFS. Robustness of the PFS hazard ratio estimate to the adjustment for various prognostic factors in the stratified Cox model including prior chemotherapy use (yes vs. no), performance status (0 vs. 1 or 2), presence of bone lesions only at baseline (yes vs. no), time since first diagnosis of metastasis/recurrence to randomization (< 6 months vs. ≥ 6 months), non-steroidal aromatase inhibitor (NSAI) (letrozole or anastrozole) use (adjuvant vs. metastatic setting), number of organs involved (1 vs. 2 vs. ≥3 – to be adapted depending on the number of patients in each category), and PgR status (positive vs. negative) will be assessed. The strata will be based on stratification information obtained through IRT. A revised multivariate stratified cox model including the key prognostic factors as well as the baseline covariates where imbalances between arms have been observed will be provided: performance status (0 vs. 1 or 2), presence of bone lesions only at baseline (yes vs. no), number of organs involved (1 vs. 2 vs. ≥3), prior chemotherapy use (yes vs. no), age (<65 years vs. ≥65 years old) and Race (Caucasian vs. non-caucasian).

Further supportive analyses will include:

- Number of patients with a PFS event and number of patients censored for the PFS analysis will be summarized. In addition, a summary of reasons for PFS censoring will be provided by treatment arm. The following categories will be used as appropriate (based on the end of treatment page, the study evaluation completion page and the survival page and based on the distance D2 defined in [Section 2.5.5](#)):
 - Ongoing without event
 - Adequate assessment no longer available (when follow-up for progression is stopped at a certain time or interrupted for a certain time period before cut-off for any reason, e.g., due to loss to follow-up or consent withdrawal)
 - New cancer therapy added
 - Event documented after two or more missing tumor assessments (for primary analysis only)
- Timing of all tumor assessments will be depicted graphically as per local radiology review by treatment arm
- 95% confidence intervals will be provided for all estimates of the main primary analysis (i.e. median, survival probabilities and hazard ratio)

